- **Aim 3**: To explore the impact of digital CBT-I on birth outcomes. In response to research indicating that insomnia and poor sleep quality are associated with increased risk for preterm birth, we will compare rates of preterm birth, as well as other birth outcomes such as low birthweight, delivery method, and APGAR scores, between digital CBT-I and TAU participants. Because the sample size of the proposed study will be too small to draw conclusions, this aim is exploratory.

Trial Design

The study is a parallel group, superiority, randomized controlled trial of digital CBT-I versus TAU among pregnant women, with a 1:1 allocation ratio.

Methods

Participants, interventions, and outcomes

Study setting. All study activities will occur remotely via phone, website, and digital app.

Eligibility criteria. Inclusion criteria are: 1) self-reported pregnancy up to 28 weeks gestation, 2) 18 years of age or older, 3) meets DSM-5 criteria for insomnia disorder as determined by the Sleep Condition Indicator (women experiencing symptoms \geq 1 month are eligible in contrast to DSM-5 criteria requiring symptom duration \geq 3 months) or experiencing elevated insomnia symptom severity as determined by a total score \geq 11 on the Insomnia Severity Index, and 4) has regular access to a web-enabled computer, tablet, or smart phone. Exclusion criteria are: 1) probable major depression as determined by a total score \geq 15 on the Edinburgh Postnatal Depression Scale (EPDS), 2) self-reported bipolar disorder, 3) self-reported history of psychosis, 4) active suicidality defined as scoring > 1 on EPDS item 10, or report of a specific suicide plan or recent attempt, and 5) shift work employee.

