Outcomes. The primary outcome is change in insomnia symptom severity (Insomnia Severity Index) from baseline to 10-weeks post-randomization. Secondary sleep outcomes include sleep efficiency (sleep diary), sleep duration (sleep diary), global sleep quality (Pittsburgh Sleep Quality Index), and insomnia caseness (Sleep Condition Indicator). Secondary mental health outcomes include depressive symptom severity (Edinburgh Postnatal Depression Scale) and anxiety (Generalized Anxiety Disorder Scale). We will additionally examine change to 18-weeks post-randomization, 36 weeks gestation, 3 months postpartum, and 6 months postpartum. Other, exploratory outcomes include birth outcomes, such as gestational age at delivery, APGAR scores, birthweight, and delivery method.

Participant timeline (See Figure). *Eligibility survey.* Individuals interested in participating will complete an electronic consent form describing the screening procedures. Next, participants will complete questionnaires to assess eligibility. Participants will complete a demographic measure, provide contact information, and indicate whether they agreed to be contacted for other research studies. Individuals who pass the eligibility survey will complete the study consent form and be given instructions to complete the sleep diaries.

Sleep diaries. Participants will receive email requests to complete sleep diaries on REDCap for seven consecutive days. Participants will indicate when they got in bed, how long it took to fall asleep, number of awakenings, duration of awakenings, final awakening time, and when they got out of bed. Participants who complete at least four diaries will be eligible to proceed to the orientation session.

Orientation. The primary goal of the phone orientation session, modeled after Goldberg and Kiernan (2005),¹⁵ is to promote participant retention by discussing the importance of the trial, required commitments, what to expect if randomized to digital CBT-I or TAU, the rationale of the control condition and random assignment, and the impact of attrition bias. Participants will describe personal pros and cons for participating in the trial, and will be given as much time as needed to decide whether to participate.

Baseline measures. Participants will complete baseline measures on the Qualtrics online survey system.

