Randomization. Upon the participant's completion of the baseline measures, study staff will request the condition assignment from the independent investigator who generated the randomization sequence. Study staff will inform participants of their condition assignment by phone call and email.

Follow-up assessments. Participants will complete all study measures and the daily sleep diaries at 10-weeks post-randomization, and all study measures at 18-weeks post-randomization, 36 weeks gestation, 3 months postpartum, and 6 months postpartum.

Sample size. Existing literature comparing CBT-I to treatment as usual suggests a large effect size (Cohen's d=0.95) for baseline to post-intervention differences and a medium effect size (Cohen's d=0.69) for baseline to 8-week follow-up on sleep efficiency.¹³ As for depression symptom severity, existing literature comparing CBT-I to treatment as usual suggests a small to medium effect size (Cohen's d=0.20-0.69) for baseline to post-intervention differences and a medium effect size (Cohen's d=0.48-0.78) for baseline to 8-week follow-up.^{9,14} Using G*Power for an ANOVA repeated measures with a within-between interaction, we estimated that 128 women were required to have 80% power to detect a small-to-medium effect size (Cohen's d=.30) with α =.01 for a within-between interaction. Attrition in web-based CBT-I programs ranges from 4-22%.^{13,16,17} but a meta-analysis of computer-based treatments for depression estimated drop-out rates of 38.4% in programs that offer administrative support. ¹⁸ We used the higher attrition estimate of 38%, yielding a required sample size of 208 participants (n=104 per group).

Recruitment. We will utilize several recruitment methods to meet our target sample size. Although recruitment will focus mainly on the Bay Area, participants can enroll from anywhere because all study activities are completed remotely.

UCSF Outpatient Recruitment Program. Study recruiters will review medical records of women receiving prenatal care at UCSF. Women who may be eligible based off chart review (e.g., less than 28 weeks pregnant) will be approached in the clinic waiting area at the time of their appointment to be introduced to the study. Recruiters will give the patient an opt-in card

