Statistical methods. Independent samples t-tests and chi-square tests will be used to examine between-group differences in baseline sociodemographic and clinical characteristics. Linear mixed effects models will be used to examine whether within-woman changes in sleep and mental health outcomes differ between the digital CBT-I and treatment as usual groups. 30 Models will include the sleep and mental health outcomes as the dependent variables, along with time, intervention group, and time by group interactions as the predictors. The models also will include random intercepts to accommodate the correlation among the repeated responses within women. The regression coefficients of time by intervention group interactions measure the differences in the rate of within-woman change in the outcomes between the two intervention groups. We will assess the statistical significance of the time by intervention group interaction using likelihood ratio tests. The primary analysis will assess differences in changes in insomnia symptom severity from baseline to post-intervention with time measured in weeks. Secondary analyses of additional sleep and mental health outcomes will use the same time scale. Additionally, we will examine change from baseline to follow-up.

Monitoring

Harms. Adverse events that are spontaneously reported by participants will be characterized by an independent safety officer as unexpected or expected, and causes will be characterized as definitely related, probably related, possibly related, or unrelated to study participation. Adverse events that are determined to be unrelated to study participation are documented but not reported to the IRB. All other adverse events are reported to the IRB.

Ethics and Dissemination

Research ethics approval

The research protocol will be submitted to the UCSF institutional review board for approval.

Protocol amendments

Protocol modifications will be communicated to all study investigators and approved by the IRB prior to implementation, and the trial registry will be updated accordingly.

Consent or assent

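### Random intercepts are the only within-woman covariance the plan states; if follow-up visits to 6 months postpartum are pooled in that model, late-change standard errors may be too small

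*Combined protocol and SAP*

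**What the plan says.** The Statistical methods section specifies linear mixed models with time, group and their interaction. On within-woman dependence it says: "The models also will include random intercepts to accommodate the correlation among the repeated responses within women". It names no random slope, serial or unstructured covariance, or robust standard error. The test is also given: "We will assess the statistical significance of the time by intervention group interaction using likelihood ratio tests".

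The primary analysis covers two visits: "The primary analysis will assess differences in changes in insomnia symptom severity from baseline to post-intervention with time measured in weeks". The later visits get one sentence: "Additionally, we will examine change from baseline to follow-up". The Outcomes section lists them: "We will additionally examine change to 18-weeks post-randomization, 36 weeks gestation, 3 months postpartum, and 6 months postpartum". With baseline and week 10 this makes six visits. The text does not say whether the later visits enter one joint model or are each compared with baseline separately, nor whether time is linear or categorical there.

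The only significance level in the documents is in the Sample size paragraph, where the design is sized to "detect a small-to-medium effect size (Cohen's d=.30) with α =.01 for a within-between interaction". No level is set for the analyses themselves.

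**The concern.** A random intercept with a single residual variance implies equal variance at every visit and equal correlation between any two visits. With two visits that is harmless. Across six visits, from pregnancy through birth to half a year afterwards, it says that scores 8 weeks apart are no more alike than scores many months apart. The plan neither defends this assumption nor proposes to check it.

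If correlation falls with distance, the model applies one averaged correlation to all pairs. That average is too high for baseline against the last visit and too low for baseline against week 10. Late contrasts then look more precise than they are, and early ones less so. Coding visits as categories does not cure this, because the fault lies in the covariance and not in the mean.

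Any claim that a benefit lasts into late pregnancy or the postpartum period would rest on these tests.

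**Working it through.** The documents state no error rate for the follow-up tests, so there is no figure of the plan's own to reproduce.

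**Inputs from the documents.** Six visits (Outcomes; Follow-up assessments); random intercepts and likelihood ratio tests (Statistical methods); 208 women, 104 per arm, with 38% attrition planned (Sample size); entry at "self-reported pregnancy up to 28 weeks gestation" (Eligibility criteria).

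**Assumptions.** Visits at weeks 0, 10, 18, 24, 41 and 54, which is a woman randomized near 12 weeks' gestation who delivers at term. Equal variances. Correlation falling linearly from .60 at an 8-week gap to ρ_L = .45, .35 or .25 at 54 weeks:

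r(d) = .60 − (.60 − ρ_L)(d − 8)/46.

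**Step 1: the pooled correlation.** With complete data the random-intercept fit settles on the mean of the 15 pairwise correlations. The mean gap is 369/15 = 24.6 weeks, so ρ̄ = .60 − (.60 − ρ_L)(16.6/46) = .546, .510 or .474.

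**Step 2: true over model-based standard error.** For change from baseline to visit k, q = √[(1 − ρ_0k)/(1 − ρ̄)]. For the linear slope, with c the centred visit times and R the true correlation matrix, q = √[c′Rc / ((1 − ρ̄) c′c)].

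**Step 3: actual test size.** Size = 2Φ(−z/q), with z = 1.960 at 5% and 2.576 at 1%. Example for ρ_L = .35, last visit: q = √(.65/.490) = 1.151; 1.960/1.151 = 1.70; size 8.9%.

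| ρ_L | Last visit: q, size at 5%, at 1% | Slope in weeks: q, size at 5%, at 1% | Week 10: q, size at 5% |
|---|---|---|---|
| .45 | 1.10, 7.5%, 1.9% | 1.18, 9.6%, 2.9% | 0.95, 3.8% |
| .35 | 1.15, 8.9%, 2.5% | 1.26, 12.0%, 4.1% | 0.92, 3.2% |
| .25 | 1.19, 10.1%, 3.1% | 1.33, 14.1%, 5.3% | 0.89, 2.7% |

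**Step 4: simulation.** Null trials on the same visit grid, 104 per arm, with and without 38% attrition, 1,500 per scenario:
- last visit: 7–11% at nominal 5%, 2.0–3.5% at 1%;
- linear time-by-group likelihood ratio test: 8–9%, 10–13% and 14–15% for the three decays at 5%, and 2.5–6.1% at 1%;
- week 10 in the same fit: 3–4% at 5%.

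**Step 5: sensitivity, nominal 5%.**
- Baseline SD 23% smaller, as eligibility cut-offs might produce: last visit 5.6–7.7%, slope 8.6–12.8%.
- Non-linear mean path common to both arms: slope 6–10%.
- Entry at week 27: last visit 7.0–9.2%, slope 8.2–11.7%.
- Other covariance shapes, with visits at weeks 0, 10, 18, 20, 34 and 48: last visit from 5.4% (random slopes) to 17.5% (pure exponential decay); slope from 5.6% to 24%.
- Joint five-degree-of-freedom test with categorical time: 5–10%.
- Constant correlation: 4.3–6.3% simulated, consistent with no error.
- Random-intercept model on baseline and the last visit only: 4.6–6.6%, consistent with no error.
- All six visits with woman-clustered robust standard errors: 4.0–6.2%.

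**The case against.** The strongest reply is that the plan never says the visits are pooled. The Outcomes section speaks of change to each visit, and the primary analysis is itself a two-visit change, so separate two-visit models are a natural reading. On that reading the inflation vanishes. This stands, and it makes the point conditional. What remains then is a loss of information: intermediate visits go unused for women who miss the visit being tested, which matters with 38% attrition planned.

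A reader might infer more than the documents support:
- *That the plan allows no other covariance.* Random intercepts are the only structure stated; nothing rules out another.
- *That the follow-up tests do run at 7–15%.* The documents give no variances or correlations and set no 5% level. The figures illustrate assumed correlations.
- *That late-visit contrasts reach 15% in this illustration.* The upper end belongs to the linear slope test under the steepest assumed decay; the late contrast stays at about 7–11%.
- *That the primary result is affected.* A two-visit analysis has only one correlation to fit.
- *That the gap from baseline to the last visit is about a year for most women.* A 52-week gap needs entry by about 14 weeks' gestation. Entry at 28 weeks gives about 38 weeks (12 to a term birth plus 26). No distribution of gestation at entry is given.

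The scope is also limited. Diaries are collected at baseline and week 10 only, so sleep efficiency and duration have no late visits, and insomnia caseness is binary.

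**Conclusion.** The point holds as a conditional one about secondary analyses. It needs two things: all visits entering one random-intercept model, and within-woman correlation that falls with time. The plan leaves the first open, and the second is plausible across pregnancy, birth and the postpartum months. Both given, and with correlation falling from .60 to .25–.45, change to 6 months postpartum tests at about 7–11% at nominal 5% and the linear interaction at about 8–15%. At 1% the figures are about 2–3.5% and 2.5–6%. Change to week 10 from the same fit is conservative. A smaller baseline variance brings the late contrast to about 6–8%, and a non-linear mean path brings the slope test to about 6–10%. The plan should be changed because the correction is standard and cheap, and loses little if correlation turns out to be constant.

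**What to change.** State in Statistical methods how the follow-up visits are analysed and at what significance level. For the continuous outcomes measured at every visit (ISI, PSQI, EPDS, GAD-7), fit one model per outcome with visit as a category, group-by-visit terms and an unstructured within-woman covariance, using REML with Kenward-Roger or Satterthwaite degrees of freedom. Read change to each visit as a contrast. Women who miss one visit and return later then still contribute.

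Name woman-clustered robust standard errors as the fallback if the model does not converge. Report them as a check in any case, because visit spacing and order depend on gestation at entry. The 36-week visit coincides with week 18 for entry at 18 weeks (36 − 18 = 18) and comes before week 10 for entry after 26 weeks. A covariance indexed by visit therefore averages over different spacings.

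Keep the diary outcomes as two-visit analyses, and analyse insomnia caseness with a binary-outcome model.

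The cost is SAP wording and a few lines of code, up to 6 × 7/2 = 21 covariance parameters estimated from 208 women, and somewhat wider intervals at late visits.

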Interventions. Digital CBT-I. The digital CBT-I program, Sleepio (www.sleepio.com), is delivered in 6 weekly web-sessions via website or iOS app. Treatment content is based on CBT-I manuals and includes a behavioral component (sleep restriction, stimulus control, and relaxation), a cognitive component (paradoxical intention, cognitive restructuring, mindfulness, positive imagery, putting the day to rest) and an educational component (psycho-education, sleep hygiene). The program is interactive, and content is presented by an animated virtual therapist. Participants schedule their session times and are prompted via email/SMS if they do not complete the session as scheduled. Participants complete daily sleep diaries throughout the intervention, which is used by the program to provide personalized help. Participants receive an email/SMS reminder each morning to prompt them to fill in their sleep diary. Additionally, study staff will monitor participant use of the website, and will contact any participants who have not logged on to the program or who have fallen behind in weekly sessions in order to discuss any challenges and troubleshoot barriers. Participants complete a short questionnaire at the beginning of the intervention to set treatment goals. Throughout the course of therapy, participants have access to an online community board and an online library of information about sleep. Participants will receive access to Sleepio at no cost as part of their participation.

Treatment as usual (TAU). The control condition is intended to reflect standard care for pregnant women with insomnia symptoms. No limits are placed on receiving non-study treatment, including medication or psychotherapy. Participants randomized to TAU will receive a free voucher code to Sleepio upon study completion.

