Electronic health record recruitment. MyChart (APeX) will conduct a search for patients based on the study's inclusion and exclusion criteria. This is a completely computer-aided search, meaning the computer— not a person— searches patient charts. When a patient is identified as potentially eligible, they will receive an email from MyChart that asks them to log in to MyChart to read about a study in which they might be interested. The email is short and is the same for every recipient—it contains no patient-specific or study-specific information. When the patient logs into MyChart, there will be a "Research" tab with template information about research participation and how to opt out of receiving recruitment messages. The patient can click through to learn about the specific study to which they have been matched. The patient has the option of clicking a button to let the study team know that they are interested in learning more about the study. The study team will only receive information about the patient if the patient takes this action. If the patient clicks "No thanks" or simply does not respond, they will not be contacted by the study team or receive any follow-up emails from MyChart about the study, nor will their information be shared with the study team.

Assignment of interventions

Allocation. The blocked randomization sequence will be generated by an independent investigator using Sealed Envelope.²⁰ The randomization sequence and block sizes will be concealed from study staff. The randomization sequence will be kept on an electronic file inaccessible to the study staff. Once a participant completes baseline measures, study staff will request the allocation assignment from the independent investigator. Study investigators and staff will not be able to influence randomization or have access to future allocations.

Blinding. For study administration purposes, staff will be unblinded to participant condition assignment after allocation. Study staff will be blinded to outcomes during the trial. Participants will be unblinded to condition assignment due to the nature of the comparison group, which is not an active comparator. The study statistician will remain blinded to condition assignment for all primary analyses.

Data collection, management, and analysis

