Data collection methods. Participants will complete study measures using the Qualtrics amd REDcap survey systems, which allow participants to read questions on the screen and press the response buttons to answer. Response validation will be utilized so that participants can only enter values within range for each item. To reduce missing data, responses will be requested for each item.

Subjective sleep outcomes. The primary efficacy outcome is insomnia symptom severity, as measured by the total score on the Insomnia Severity Index (ISI). 21,22 The ISI is a seven item measure that assesses symptom severity, satisfaction with sleep, impairment caused by symptoms, distress caused by symptoms, and the extent to which others have noticed symptoms over the last two weeks. A total score is computed by summing all items. Scores ≤ 7 indicate no

clinically significant insomnia, 8-14 indicate subthreshold insomnia, 15-21 indicate moderate severity insomnia, and \geq 22 indicate severe insomnia.

Secondary sleep outcomes are sleep efficiency, nightly sleep duration, global sleep quality, and insomnia diagnosis. Daily sleep diaries will be used to measure sleep efficiency and sleep duration. Sleep efficiency is calculated by dividing the amount of time sleeping in bed by the total amount of time spent in bed and multiplying by 100. Scores range from 0-100%, with 85% and above considered normal. Sleep duration is the total amount of nightly sleep in hours. Global sleep quality will be measured using the Pittsburgh Sleep Quality Index (PSQI), a 19-item measure comprised of seven components assessing sleep duration, disturbance, latency, efficiency, quality, days of dysfunction due to sleepiness, and needing medication to sleep. ²³ Each component score ranges from 0-3, and the components are summed to create a PSQI global sleep quality score ranging from 0-21. Higher scores indicate worse global sleep quality, and scores above 5 indicate poor sleep. To measure possible cases of DSM-5 insomnia disorder, we will use the Sleep Condition Indicator (SCI). ²⁴ By adding a ninth item to assess early-morning awakening, the Sleep Condition Indicator can be used to identify possible cases of DSM-5 insomnia disorder. ²⁴

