Mental health outcomes. Depressive symptom severity will be assessed using the Edinburgh Postnatal Depression Scale (EPDS).²⁵ The EPDS is a 10-item self-report measure that omits depressive symptoms that can be conflated with normal pregnancy symptoms (e.g., appetite disturbance). It is frequently used to assess depressive symptom severity during pregnancy. Total scores range from 0-30, with higher scores indicating higher symptom severity. Scores of 10 or greater suggest minor depression, and scores of 15 or greater suggest major depression among pregnant women.²⁶ Anxiety symptom severity will be assessed using the Generalized Anxiety Disorder Scale (GAD-7).²⁷ Scores range from 0-21 with higher scores indicating higher anxiety symptom severity. Scores of 0-4 suggest minimal anxiety, 5-9 suggest mild anxiety, 10-14 suggest moderate anxiety, and 11-21 suggest severe anxiety.

All study measures will e self-report and collected via online survey systems. With the exception of the sleep diaries, which will be collected via REDCap, study measures will be administered via Qualtrics.

Use of non-study treatments. At each follow-up assessment, participants will be asked about their use of the following aids to improve sleep: sleep medication prescribed by a doctor; combination sleep aid and pain reliever; over-the-counter or store-bought sleep aid; alternative therapy or herbal supplement; therapy or counseling; alcohol, beer, or wine; eyemask or ear plugs; other. Participants were also asked about their use of the following aids to improve mood: antidepressant medication, therapy or counseling; support group; alternative therapy or herbal supplements; other. Response options are 'rarely or never,' 'a few nights a month,' 'a few nights a week,' and 'every night/almost every night.'

Obstetric outcomes. Obstetric outcomes will be assessed via medical record review, and include but are not limited to the following outcomes: gestational age at delivery, APGAR scores, birthweight, and delivery method. Participants will also self-report birth outcomes in case we are not able to obtain their medical record data.^{28,29}

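### Spontaneous report is the only adverse-event route described; one identical question in both arms' existing follow-up surveys would narrow the gap at small cost

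*Combined protocol and SAP*

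**What the plan says.** Under Monitoring, the Harms paragraph gives one route by which an adverse event enters the trial's records: "Adverse events that are spontaneously reported by participants will be characterized by an independent safety officer". It then covers expectedness, relatedness to participation and which events go to the IRB. It names no question, checklist or schedule for asking about events.

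Under Interventions, the digital CBT-I program "is delivered in 6 weekly web-sessions via website or iOS app", and its behavioral component includes sleep restriction. Staff monitor use of the program and contact participants who have not logged on, or "who have fallen behind in weekly sessions in order to discuss any challenges and troubleshoot barriers". The treatment-as-usual (TAU) paragraph describes no corresponding contact.

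Under Follow-up assessments, both arms have the same five follow-ups: 10 and 18 weeks after randomization, 36 weeks of gestation, and 3 and 6 months after birth. For the first of these: "Participants will complete all study measures and the daily sleep diaries at 10-weeks post-randomization". Study measures other than the diaries are on one online survey platform.

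Much that bears on safety is already collected in both arms. The PSQI includes "days of dysfunction due to sleepiness, and needing medication to sleep". The EPDS and GAD-7 cover mood and anxiety. On treatments used: "At each follow-up assessment, participants will be asked about their use of the following aids to improve sleep", with a similar list for mood. Obstetric outcomes come from medical records, with self-reported birth outcomes as back-up.

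Under Blinding: "Study staff will be blinded to outcomes during the trial".

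**The concern.** Spontaneous reporting records what a participant chooses to mention, when she has an occasion to mention it. In a fully remote trial there is no clinic visit at which an event would come up. For anything the scheduled measures do not cover, the only described input to the safety officer, and through that officer to the IRB, is therefore what a woman volunteers. An injury, or a medical event outside the obstetric record, would be an example (mine, not the protocol's).

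Two things are at stake. First, a short list of reports could be read as evidence of few harms when it may reflect only that nobody asked. Second, some women in one arm have an extra conversation with staff about difficulties with the program. If counts were shown by arm, a reader could not separate a real difference from a difference in opportunity to report.

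**Working it through.** The plan gives no adverse-event rate or capture rate, so there is no figure to reproduce. The check is a comparison of sections, followed by a test of whether any size can be derived.

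**1. Routes by which an event could reach the safety officer**

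- Spontaneous report (Harms): both arms; the only route named.
- Staff contact about non-use or falling behind (Interventions): digital CBT-I only, and only a subset. Its mode is not stated, and it is not described as an enquiry about harms.
- Invitation to contact the principal investigator (Consent): both arms.
- Reminders after non-response (Data collection methods): both arms.
- Solicited adverse-event question: none described.

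Equal opportunity to report is therefore not shown.

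**2. What is already covered**

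Sleep and daytime dysfunction, mood, anxiety, aid use and obstetric outcomes are collected on the same schedule in both arms. The Consent section describes authorization to obtain prenatal and delivery records only for women recruited through the UCSF clinics, while Recruitment allows enrolment from anywhere. The self-report back-up is for birth outcomes. What remains is other events. No section sends the scheduled measures to the safety officer.

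**3. Can a between-arm distortion be sized?**

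Let p be the true proportion of women with an event, equal in both arms, and let c1 and c0 be the proportions of events reported under CBT-I and TAU.

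Apparent risk ratio = (p × c1) / (p × c0) = c1 / c0

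The result is simply the assumed capture ratio:

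- c1 = c0: ratio 1.0
- c1 = 40%, c0 = 30%: 0.40 / 0.30 = 1.33
- c1 = 50%, c0 = 25%: 0.50 / 0.25 = 2.0
- those last rates exchanged: 0.25 / 0.50 = 0.5

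The documents give neither c1 nor c0, so all four are assumptions. The existence, direction and size of a distortion stay unknown.

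**4. How far would a survey question reach?**

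Sample size plans for 208 women and cites attrition of 4% to 22% in web-based CBT-I, adopting 38%. Applying each rate to a single survey, which is my assumption:

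- 208 × 0.96 = 200
- 208 × 0.78 = 162
- 208 × 0.62 = 129

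These are upper limits on the women who would answer, because some of those retained may return only the primary outcome measure, by mail or as the shortened option.

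**5. Recall**

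The first interval is 10 weeks for a woman whose first survey is the 10-week one. From 3 to 6 months after birth is 3 × 52 / 12 = 13 weeks. Recall may therefore span 10 weeks or more.

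**6. Timing**

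The amendment of March 27, 2018 reports 183 of 208 women randomized: 183 / 208 = 88%. Ten weeks (70 days) after that date is June 5, 2018, so the 10-week survey was due by then for those women. The reference list of the current text cites a 2019 publication. The documents do not say when the last follow-up ended.

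**The case against.** The strongest reply is that nothing here is an error. Harms are not among the aims, outcomes or planned analyses. No between-arm adverse-event comparison is specified, and the primary ISI analysis does not depend on adverse-event capture. The measures both arms complete already cover much of what one would want to know about a sleep intervention in pregnancy. All of this stands, and it makes the point a cheap improvement and not a flaw in the primary inference. It does not answer the remaining gap: other events have no route except being volunteered, and the trial will still be expected to say something about harms.

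A second reply is that the staff contact concerns use of the program, involves only some women, and sits beside routes open to both arms. That also stands. A reader might infer from the contact that CBT-I events will be over-reported, or that arm counts will be biased by some stated factor. The documents do not support this, because they give no capture rates and do not say that harms are discussed in those contacts.

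A third reply is that the supplied text is incomplete: the consent forms and the surveys themselves are not included. The finding is accordingly about what the protocol text describes. If the surveys already carry such a question, the Harms paragraph should say so.

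A fourth reply is that the remedy may come too late. That is a fair reading of the amendment dates, and it is why the fix has a second branch.

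**Conclusion.** The point holds as a low-cost improvement to harms capture. In the supplied text, spontaneous report is the only adverse-event route, and equal opportunity to report is not shown because one arm alone has staff contact about difficulties with the program. For events outside the scheduled measures, capture is likely incomplete. Neither the share missed nor any tilt between arms can be derived.

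Three further inferences should be resisted:

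- That the trial collects no safety information. It collects a good deal, in both arms.
- That the efficacy result is compromised. The ISI analysis is untouched.
- That a survey question would close the gap. It would not reach women who return only the primary-outcome form or no survey, and it relies on recall over 10 weeks or more.

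The conclusion assumes that no solicited question exists in instruments not supplied. How much of the fix is still usable depends on whether follow-up was open when the text was reviewed, which the documents do not settle.

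**What to change.** If follow-up is open:

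- Add one short adverse-event question, worded identically in both arms, to the existing online follow-up surveys, covering the time since the previous survey.
- Send the answers to the independent safety officer, so that study staff stay blinded to outcomes, and state how often they are read.
- Report solicited and spontaneous events separately by arm, with the number of women who answered, and mark events first raised in contacts about program use.
- Leave the mailed and shortened primary-outcome forms unchanged, to protect return of the primary outcome.

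The cost is an IRB amendment, survey access for the safety officer (Data management limits that platform's data to the survey owner), slightly longer surveys, prompt reading of answers and more events to classify. No new visit or platform is needed.

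If follow-up has closed, state in the report that adverse events were captured only by spontaneous report, and that the counts support neither a between-arm harms comparison nor a claim of few or no harms. Flag any existing reports that arose in contacts about program use, where this was recorded. The cost is one limitation sentence and that flag.
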